## Study Summary

Title	Preoperative Magnetic Resonance as an Alternative to Computed Tomography Three-Dimensional Imaging for Characterizing Bone Loss in Shoulder Arthroplasty Candidates with Glenohumeral Osteoarthritis: A prospective, blinded, and controlled clinical trial.
Short Title	3D MR versus 3D CT in Glenohumeral Osteoarthritis
Protocol Number	S17-00500
Methodology	A prospective, unrandomized, single-blinded, self-controlled, and single-armed diagnostic radiological evaluation study.
Study Duration	12-Months
Study Center(s)	Single-Center
Purpose	To examine the non-inferiority of three-dimensional (3D) magnetic resonance (MR) versus the gold-standard, 3D computed tomography (CT) imaging, in the analysis of bone loss in shoulder arthroplasty (SA) candidates with glenohumeral osteoarthritis (OA). This study does not assess the safety and efficacy of MR imaging for musculoskeletal disorders.
Number of Subjects	50 subjects
Diagnosis and Main Inclusion Criteria	Patients with glenohumeral OA who are candidates for SA based on clinical examination with radiographic evidence of significant glenoid wear ; males and females age 18 and above.
Study Intervention and Planned Use	3D MR imaging of the shoulder for evaluation of glenoid bone loss.
Reference Intervention	3D CT imaging of the shoulder for evaluation of glenoid bone loss.
Statistical Methodology	Paired sample t-test to compare measurements by model and ANOVA to assess differences among modalities.

CONFIDENTIAL

This material is the property of the NYU School of Medicine and Langone Medical Center.  
Do not disclose or use except as authorized in writing by the study sponsor (if applicable).

## I. PURPOSE OF THE STUDY AND BACKGROUND

### **Purpose**

The purpose of this study is to examine the noninferiority of 3-dimensional (3D) magnetic resonance (MR) as an alternative to 3D computed tomography (CT) imaging to characterize glenoid bone loss in shoulder arthroplasty (SA) candidates with glenohumeral osteoarthritis and radiographic evidence of severe glenoid erosion. MR has been routinely used in musculoskeletal imaging with and without contrast. This study employs no non-FDA approved investigational MRI hardware or software.

### **Background & Study Rationale**

There has been over a five-fold growth in incidence of shoulder arthroplasty (SA) for glenohumeral osteoarthritis (OA) since 2000 (1) (2) (3) (4). Asymmetric glenoid erosion may occur in glenohumeral OA (5). Patient-specific variations in magnitude and retroversion of glenoid bone loss in glenohumeral osteoarthritis pose a challenge for orthopaedic surgeons in joint reconstruction (6). Eccentric loading of the glenohumeral joint may lead to glenoid loosening which potentially requires revision surgery (7). Moreover, posterior glenoid erosion is a risk factor for poorer outcomes in function and pain (8) (9) (10). The management of glenoid erosion in shoulder arthroplasty demands individualized surgical techniques as well as implants to optimize outcomes and maximize implant longevity. Surgical techniques to address glenoid retroversion include eccentric reaming, glenoid bone grafts, augmented glenoid components, total shoulder arthroplasty, or specialized implants (7) (11). The “gold-standard” modality for assessment of complex glenoid anatomy to assist with surgical planning is 3D CT imaging (9) (12) (13). However, CT imaging exposes patients to radiation. Recently, 3D MR has been developed to characterize glenoid bone loss (14).

There is significant variation in glenoid morphology among patients with glenohumeral OA. Prior studies have discussed higher distributions of patients with glenoids who had posterior erosion and/or retroversion (15-18). To better guide treatment approaches, Walch et al. described glenoid morphology using CT scans in 113 shoulders between 1988 and 1995 (19). Specifically, the authors developed three broad classification types based on humeral head position, glenoid retroversion, and erosion pattern: Type A, Type B, and Type C. Types A and B have subgroups based on severity.

Three-dimensional reconstruction of CT images at the glenohumeral joint have reliably assisted surgeons with preoperative planning whereas two-dimensional (2-D) radiographs and CT scans may misrepresent important anatomical characteristics of the shoulder leading to insufficient evaluation of erosion (12) (13).

To mitigate radiation exposure from 3D CT, 3D MR could serve as an alternative for patients with end-stage glenohumeral OA indicated for shoulder reconstruction.

### **Study Design**

Prospective, unrandomized, double blinded, self-controlled clinical trial

### **Objective**

1. The primary objective is to evaluate the noninferiority of 3D MR when compared to 3D CT for characterizing bone morphology in patients with glenohumeral osteoarthritis.

### **Hypothesis**

3D MR imaging provides the same information as 3D CT in characterizing glenoid morphology.

### **Primary Endpoints**

- Differences and/or similarities in glenoid erosion and version measurements between of 3D CT and 3D MR.

### **Outcome Measure Evaluation Criteria**

- Degree of concordance/discordance between interpretation from 3D CT and 3D MR

CONFIDENTIAL

This material is the property of the NYU School of Medicine and Langone Medical Center.  
Do not disclose or use except as authorized in writing by the study sponsor (if applicable).

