##### Visit 2 -- Preoperative Imaging:

Subjects will have both 3D CT and 3D non-contrast MR scheduled on the same day. The CT scan, which is standard of care, will be scheduled at NYU Langone Orthopedic Hospital followed by the MR, the investigational procedure, at NYU Langone Orthopedic Center. Before imaging, the subjects will be screened for potential contraindications to each imaging modality in accordance with institutional standard of care routine procedures. The standard of care CT imaging will take no more than 30 minutes while the investigational MR imaging will take no more than 60 minutes in duration. Each enrolled subject will receive a standard of care CT scan along with an investigational MRI scan of the shoulder girdle while supine. Each enrolled subject's CT imaging is not dependent on receiving prior MR imaging; he/she will not experience delays in receiving standard of care CT imaging as a result of study participation.

The CT protocol consists of 3-mm axial images of the glenoid reconstructed into 1-mm sagittal and coronal 2D reconstructions using the following parameters: 120 kV, 280 mA, and pitch of 0.9. The CT data were also used to produce a 3D reconstruction of each glenoid.

The 2D glenoid version is measured by 2 musculoskeletal-trained radiologists on 2 occasions, at a minimum of 2 weeks apart, with the observers blinded to each other's results. The 2 observers meet before obtaining data to review the appropriate technique for measuring glenoid version. The 2D glenoid version is determined using the method of Friedman et al (17) with the mid glenoid cut being determined by dividing the total number of axial cuts through the glenoid by 2 (20).

The 2D CT images are imported in Vitrea software. The 3D volume rendering model will be produced. The 3D glenoid version is measured by the same 2 observers on 2 occasions, at a minimum of 2 weeks apart, with the observers blinded to each other's results. Three points which were previously validated were first interactively placed on the Mimics 3D model by the observer: the inferior tip of the scapula body, the center of the glenoid surface, and the medial pole of the scapula, as described by Kwon et al. (12) As described in detail below, these points were used to define the transverse scapular plane, based

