The 3D MRI glenoid version is measured by the two observers with the same method used for CT 3D glenoid version measurement following generating a new 2D axial MR images from the 3D MRI model using the three-point method as described above.

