### **Data Analysis**

Using SAS software, version 9.4 (SAS Institute Inc., Cary, NC, USA) Paired sample t-test to compare measurements by model and ANOVA to assess differences among modalities.

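### Concordance between 3D CT and 3D MR is the evaluation criterion, but the named tests address mean differences only, so patient-level agreement is not measured

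*Combined protocol and SAP*

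**What the plan says.** Section I sets the target in four places.

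- The yardstick for the comparison is given as "Degree of concordance/discordance between interpretation from 3D CT and 3D MR" (under Outcome Measure Evaluation Criteria).
- The aim is put this way: "The primary objective is to evaluate the noninferiority of 3D MR when compared to 3D CT for characterizing bone morphology" (under Objective).
- The endpoint is worded as "Differences and/or similarities in glenoid erosion and version measurements between of 3D CT and 3D MR" (under Primary Endpoints).
- The claim to be examined is that "3D MR imaging provides the same information as 3D CT in characterizing glenoid morphology" (under Hypothesis).

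The background gives the intended use: "3D MR could serve as an alternative for patients with end-stage glenohumeral OA indicated for shoulder reconstruction".

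The analysis is one statement, worded identically in the Study Summary (Statistical Methodology) and in Data Analysis: "Paired sample t-test to compare measurements by model and ANOVA to assess differences among modalities". The Sample Size Analysis also rests on a paired t-test (alpha .05, power .80, a minimum of ten pairs). Planned enrolment is 50.

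For the readings, Visit 2 says of CT: "The 3D glenoid version is measured by the same 2 observers on 2 occasions, at a minimum of 2 weeks apart". For MR it says: "The 3D MRI glenoid version is measured by the two observers with the same method used for CT 3D glenoid version measurement". No statistic is attached to the repeat readings. The text supplied names no limits of agreement, intraclass correlation, concordance coefficient, kappa, equivalence test, margin or success rule.

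**The concern.** If MR is to replace CT before shoulder reconstruction, what counts is how far the two measurements differ in a given shoulder. A test of the mean difference lets over-reads and under-reads cancel. It can report no significant difference when the two modalities disagree widely patient by patient, and the likely misreading of that result as evidence of sameness favours MR. In the other direction, a very small but consistent offset could be significant and clinically trivial, and the plan has no yardstick to say so. Followed exactly, the plan cannot answer the question that its evaluation criterion asks.

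**Working it through.** **Inputs from the documents:** 50 patients (Number of Subjects); paired t-test, alpha .05, power .80, ten pairs (Sample Size Analysis). **Not in the documents, so assumed:** the SD of the MR-CT differences in glenoid version, the true bias, a 5-degree cut-off, normally distributed differences, and two-sided testing.

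**1. The plan's own figure.** Ten pairs cannot be derived forward, because no effect size, SD or sidedness is given. Working backwards with the exact two-sided paired t-test, a mean difference of 1.0 SD of the differences gives 10 pairs with power 0.803. So the figure is consistent with detecting a mean shift of about one SD. It is not a calculation about agreement.

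**2. What each passage calls for.** Concordance and sameness need the spread of individual differences as well as their mean. The t-test gives the mean. The ANOVA is assigned to differences among modalities, with no factors or variance components named. Neither is assigned to spread.

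**3. Zero bias, n = 50.** The t-test is non-significant 95% of the time at any SD, by construction. The share of patients beyond 5 degrees is 2 × (1 − Φ(5/SD)). The confidence interval for the mean has half-width t(0.975, 49) × SD/√50, with t = 2.010. The limits of agreement are ±1.96 × SD.

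| SD (degrees) | Patients beyond 5 degrees | 95% CI for mean | 95% limits of agreement |
|---|---|---|---|
| 4 | 21% | ±1.14 | ±7.84 |
| 5 | 32% | ±1.42 | ±9.80 |
| 6 | 40% | ±1.71 | ±11.76 |

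A simulation with zero bias and n = 50 makes the same point. With a CT-MR correlation of 0, 0.5 or 0.95, the t-test was non-significant in 0.949, 0.950 and 0.948 of trials. The limits of agreement were ±2.77, ±1.96 and ±0.62 between-patient SDs.

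**4. Bias of 1 degree, n = 50.** Power comes from the noncentral t with 49 df and noncentrality √50/SD. The share beyond 5 degrees is 1 − Φ(4/SD) + Φ(−6/SD).

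| SD (degrees) | Noncentrality | Power | Patients beyond 5 degrees |
|---|---|---|---|
| 2 | 3.54 | 93% | 2.4% |
| 4 | 1.77 | 41% | 22.5% |
| 6 | 1.18 | 21% | 41% |
| 10 | 0.71 | 11% | 62% |

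With a real bias, more scatter makes significance less likely while agreement gets worse.

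**5. Whether 50 pairs can support an agreement analysis.** With one difference per patient, each limit has a 95% CI half-width of t × SD × √(1/n + 1.96²/(2(n − 1))). At n = 50 this is 2.010 × √(0.0200 + 0.0392) = 0.49 SD, or about 2.0 to 2.9 degrees at SD 4 to 6.

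**The case against.** The best defence is that the named tests are not irrelevant. A paired t-test estimates bias, which is part of agreement, and it does serve the differences half of the primary endpoint. ANOVA mean squares could in principle yield an intraclass correlation. The wording is also loose: no ANOVA factors are named, and the t-test's comparison by model could cover 2D CT, 3D CT and 3D MR. All of this stands, but it does not supply an analysis of patient-level agreement, because the plan assigns the ANOVA only to differences and specifies no agreement statistic.

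Several stronger readings are tempting and should not be drawn.

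- A reader might infer that a significant result would leave the hypothesis untouched. It would not: systematic bias counts against literal sameness. What is missing is a way to say whether the bias matters.
- A reader might infer that the p-value always moves against concordance. That needs a non-zero bias. With zero bias the p-value simply carries no information about scatter.
- A reader might infer that two readers on two occasions make the limits much more precise than 0.49 SD. That treats the differences within a patient as exchangeable, whereas the CT readings cross readers with occasions. Reader effects may remove the gain.
- A reader might infer that the sample size is wrong. Ten pairs is stated as a t-test minimum, and the plan enrols 50.

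The criterion's term for what is compared could also mean a categorical reading. Limits of agreement for version alone would then not cover it. The choice of limits of agreement over an intraclass correlation as primary is likewise a judgement that the documents do not dictate.

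**Conclusion.** The concern holds. The stated question is concordance and sameness, and the only named analyses, as described, address mean differences. No planned analysis measures patient-level agreement or tests similarity, and there is no acceptable difference against which to judge a result. This is an analysis that does not fit its question, and it should be corrected before the data are analysed.

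The practical size depends on the scatter between modalities, which the documents do not give. Over the assumed SDs of 4 to 6 degrees with no bias, between a fifth and two fifths of patients could differ by more than 5 degrees while the test is non-significant 95% of the time. The 5-degree cut-off is illustrative and is not offered as a clinical threshold. The central conclusion does not rest on these values: it follows from what a test of means estimates.

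**What to change.** In Data Analysis and in the Study Summary:

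1. Make the primary analysis of 3D MR versus 3D CT glenoid version the mean MR-CT difference with its 95% CI and the 95% limits of agreement with their CIs. Treat the patient as the independent unit and use a method that allows for repeated readings by two readers.
2. Before analysis, have the investigators set and justify an acceptable difference, and state how the limits will be judged against it.
3. Keep the paired t-test as a test of bias only. An intraclass correlation or concordance coefficient may be reported in support.
4. Define what the evaluation criterion compares. If it is a categorical reading, analyse it with kappa. Apply the same agreement analysis to erosion once its measurement is defined, since the methods describe version only.

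**Cost:** analysis wording, modest programming, agreement on the acceptable difference, and possibly a less favourable result if scatter is large. The definitions in item 4 are separate work. No extra patients are needed: with 50 complete pairs and one difference per patient, each limit is known to within about 0.49 SD. Withdrawals would widen this, and no gain from multiple readings should be counted on.

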## II. CHARACTERISTICS OF THE RESEARCH POPULATION

### **Number of Subjects**

A total of fifty (50) patients will be enrolled in this study.

### **Gender of Subjects**

Men and women will be included in this study.

### **Age of Subjects**

Subjects will be at least 18 years of age.

### **Racial and Ethnic Origin**

There are no enrollment restrictions based on race or ethnic origin.

### **Inclusion Criteria**

- Males and females ages 18 or more;
- Patients suffering from glenohumeral OA;
- Radiographic evidence of severe glenoid erosion;
- Indication for TSA based on clinical exam;
- Patient is willing and able to review and sign a study informed consent form.

### **Exclusion Criteria**

- Prior arthroplasty at the affected shoulder;
- Patients with inflammatory arthritis;
- Patients with post-capsulorrhaphy arthritis;
- Patients with post-traumatic arthritis;
- Patients with rotator cuff tear arthropathy;
- Patients exhibiting a lack of physical or mental ability to perform or comply with the study procedures;
- Patients who are pregnant;
- Patients with implanted medical devices that are contraindicated to exposure up to a 3.0-tesla magnetic field.

### **Vulnerable Subjects**

Vulnerable subjects will not be enrolled.

### **Subject Withdrawal**

Patients are free to withdraw at any time from the study.

CONFIDENTIAL

This material is the property of the NYU School of Medicine and Langone Medical Center.  
Do not disclose or use except as authorized in writing by the study sponsor (if applicable).

### III. METHODS AND PROCEDURES

#### **Sample Size Analysis**

Using SAS software, version 9.4 (SAS Institute Inc., Cary, NC, USA) based on paired t-test analysis, for alpha = .05 and power = .80, ten pairs are required, at minimum, for the study.

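### The objective is noninferiority, but the only planned tests are for a difference with no margin; the .80 power for ten pairs is not power for noninferiority, and the planned 50 rests on no calculation

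*Combined protocol and SAP*

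**What the plan says.** The Objective section states: "The primary objective is to evaluate the noninferiority of 3D MR when compared to 3D CT for characterizing bone morphology". The Study Summary and the Purpose section also describe the aim as noninferiority. The Hypothesis goes further: "3D MR imaging provides the same information as 3D CT in characterizing glenoid morphology".

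The Primary Endpoints section names two measures: "Differences and/or similarities in glenoid erosion and version measurements between of 3D CT and 3D MR". The evaluation criterion is "Degree of concordance/discordance between interpretation from 3D CT and 3D MR".

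The Data Analysis section, matching the Study Summary, gives the whole statistical method: "Paired sample t-test to compare measurements by model and ANOVA to assess differences among modalities". Neither place mentions a margin or a confidence interval.

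The Sample Size Analysis is one sentence. It names the software and says that "based on paired t-test analysis, for alpha = .05 and power = .80, ten pairs are required, at minimum, for the study". Enrolment is set separately under Number of Subjects: "A total of fifty (50) patients will be enrolled in this study". Nothing links the two figures. Subject Withdrawal lets patients leave at any time, and no allowance for this is stated.

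**The concern.** Noninferiority is a claim that MR is not worse than CT by more than a stated amount. It can be tested only against that amount. A paired t-test of zero difference asks something else. If it is non-significant, the cause may be close agreement or too little data. If it is significant, the difference may still be too small to matter. The plan gives no amount, so neither result settles the objective. Because the hypothesis speaks of MR giving the same information, a non-significant result could easily be reported as success.

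The sizing has the same gap. Alpha .05 and power .80 are quoted, but power to detect what, in which measure and against which null value is not stated. A reader cannot tell what MR-CT difference either 10 or 50 pairs could rule out. Patients have an extra investigational scan with no direct benefit to themselves, so the study should be able to answer its own question.

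**Working it through.** **Inputs from the documents.** Alpha .05, power .80, paired t-test, ten pairs (Sample Size Analysis); 50 patients (Number of Subjects); each patient has both scans, so a pair is taken to be one patient (Visit 2). Not stated: difference, SD, sidedness, margin, measure sized, dropout. Everything below is therefore in SDs of the paired MR-CT differences. Results are exact (t statistic integrated over the distribution of the sample SD); normal-type approximations are shown so that they can be checked by hand.

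**1. The plan's ten pairs.** They cannot be reproduced forwards, because the effect is missing. Solved backwards for d = difference / SD at 80% power:

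| | d for n = 10 | d for n = 9 | ten is the minimum if d is about |
|---|---|---|---|
| two-sided .05 | 0.996 | 1.067 | 1.00 to 1.07 |
| one-sided .05 | 0.853 | 0.909 | 0.85 to 0.91 |

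The approximation (z for alpha + z for power)/√n gives (1.960 + 0.842)/√10 = 0.886 two-sided. It is lower than the exact value because it ignores estimation of the SD. Ten is thus a possible answer for an unstated effect of roughly one SD.

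**2. Is 50 derived from ten?** If 50 were ten inflated for dropout, 10/(1 − dropout) = 50 gives dropout = 1 − 10/50 = 80%. That is not a plausible origin, and none is stated.

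**3. What the planned test does at 50 pairs.** Approximate chance of a non-significant two-sided .05 paired t-test: Φ(2.010 − d√50).

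- d = 0.3: d√50 = 2.121; Φ(−0.111) = 0.456; exact 0.452.
- d = 0.2: d√50 = 1.414; Φ(0.596) = 0.724; exact 0.716.
- d = 0.5: exact 0.066. At the stated minimum of ten pairs the same bias gives 0.707.

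The last line shows the direction of the problem: if non-significance counts as success, the smaller sample succeeds more often.

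**4. What 50 pairs deliver against a margin.** True difference zero, 50 evaluable pairs, margin at which power is 80%:

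| test | approximation | exact |
|---|---|---|
| TOST, 5% per side | (1.677 + 1.282)/7.071 = 0.418 | 0.42 SD |
| one-sided 5% | (1.677 + 0.842)/7.071 = 0.356 | 0.36 SD |
| one-sided 2.5% | (2.010 + 0.842)/7.071 = 0.403 | 0.40 SD |

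The 2.5% level is an added alternative; the plan states only .05.

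Power with 50 pairs at assumed margins, zero bias:

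| margin | TOST | one-sided 5% | one-sided 2.5% |
|---|---|---|---|
| 0.3 SD | 35% | 67% | 55% |
| 0.5 SD | 93% | 97% | 93% |

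**5. Sensitivity of the TOST figure.**

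- With 45 or 40 evaluable pairs, the 80% margin rises from 0.42 to 0.44 or 0.47 SD.
- With 50 pairs and a 0.42 SD margin, power falls from 80% to 70% if the true bias is 0.1 SD, and to 45% if it is 0.2 SD.

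**The case against.** **Fifty is five times the stated minimum, so no shortfall is shown.** This stands. A reader might infer that ten is an arithmetic error, that 50 contradicts it, or that 50 is too few. The documents support none of these. Ten fits an effect near one SD, enrolling more than a minimum is no contradiction, and 50 gives at least 80% power if the margin is about 0.4 SD or wider, on zero bias and full evaluability. But exceeding a minimum built on an undisclosed effect says nothing about a clinically chosen margin.

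**A paired t-test can be shifted by a margin.** It can, and the Sample Size Analysis does not say that its null value is zero. That it was sized for a difference test is an inference from the analysis section. The point does not depend on it: no margin is given anywhere in the text supplied, and the planned tests are described as comparing measurements and assessing differences.

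**The 45% and 72% figures come from misreading a non-significant test, and such biases may be harmless.** The first part is right, and it is why the main repair belongs in the analysis section. The second part is open. At assumed SDs of 2, 4 or 6 degrees, 0.3 SD is 0.6, 1.2 or 1.8 degrees of version, and the documents do not say whether that matters. Only a prespecified margin can settle it.

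**Moving to equivalence would replace the stated objective.** This stands as a caution. The hypothesis and the concordance criterion lean towards a two-sided question, but the objective says noninferiority. Either form can serve if the choice is justified.

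**Conclusion.** The point holds for the analysis and for the link between sizing and objective. Followed as written, the plan cannot establish noninferiority, because it tests for a difference and sets no margin. The .80 attached to ten pairs is not a stated power for that objective, and no calculation supports the 50.

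Its practical size cannot be fixed from the documents. In SD units, 50 evaluable pairs reach 80% power at a margin of 0.36 to 0.42 SD depending on the test, with zero bias. At a 0.3 SD margin they reach only 35% to 67%. These figures assume approximately normal paired differences, one pair per patient and one measure tested alone.

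A reader might go on to infer that 50 is enough and that no further patients could be needed. That is equally unsupported until a margin and an SD are set. The missing sizing inputs would by themselves be only a reporting gap. What makes this a substantive point is that the planned test does not answer the stated objective.

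**What to change.** 1. **Data Analysis.** Make the primary analysis the confidence interval of the mean paired MR-CT difference, compared with a margin set in advance on clinical grounds for each primary measure. Use either a one-sided margin test, with the harmful direction justified, or TOST (90% interval wholly within ± the margin) if error in either direction matters. State that a non-significant t-test will not be taken as noninferiority.

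2. **Sample Size Analysis.** Stop citing ten pairs as adequate. State the measure sized, the margin, the assumed SD of the paired differences, the test and its level, and the evaluable pairs expected after withdrawal. Report the power that 50 enrolled patients give for that margin, at zero and at a non-zero true bias, and restate the power if it is below .80.

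The SD values under the working show what 50 pairs can deliver. They are not proposed margins, and copying 0.42 SD into the protocol would fit the margin to the sample size.

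**Cost.** One rewritten paragraph, a matching change to the analysis sentence (and its copy in the Study Summary), and clinical decisions on the margins and SD before results are seen. The downside is that ten can no longer be cited as adequate, and the stated power may drop below .80 if the clinical margin is under about 0.4 SD. Whether 50 suffices can be said only after those decisions.
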